16.2 Analysis Plan for Secondary Outcome and Translational Endpoint

Analyses for secondary endpoints will also be descriptive in nature. Due to the exploratory nature of this research, we will not adjust for multiple comparisons for the secondary analyses. Analyses of the motor and autonomic subscales will be identical to the analyses of the primary endpoint. Analyses of CTCAE grades and the symptom questionnaire individual items will compare the incidence and maximum (worst) values between arms. Fisher's exact tests will be used to compare incidence rates and Wilcoxon rank-sum tests will be used to compare maximum values between arms.

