2.2 Secondary Goals

Secondary endpoints include other measures of neuropathy as measured by the EORTC QLQ CIPN20 motor subscale, the EORTC QLQ CIPN20 autonomic scale, and the total CTCAE neuropathy scale. Adverse event profiles will also be assessed using symptom questionnaires and CTCAE v5.0.

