3.0 Registration Patient Eligibility

3.1 Registration - Inclusion Criteria

- 3.11 Age \geq 18 years
- 3.12 English speaking
- 3.13 Cancer diagnosis of any tumor type with chemotherapy-induced neuropathy
- 3.14 At least 4 out of 10 severity of neuropathy pain and/or tingling per appendix IV
- 3.15 Stable for at least 7 days prior to registration on medications for neuropathy, if any are being used
- 3.16 ECOG Performance Status (PS) 0, 1 or 2 (Appendix VIII).
- 3.17 **Negative pregnancy test done \leq 7 days prior to registration, for persons of childbearing potential only.**

NOTE: If a urine test is positive or cannot be confirmed as negative, a serum pregnancy test will be required.

- 3.18 Able to provide written informed consent
- 3.19a Ability to complete questionnaire(s) by themselves or with assistance.
- 3.19b No evidence of residual cancer
- 3.19c Required Initial Laboratory Values: Following completion of chemotherapy, patients must have had a CBC and serum chemistries, including the following:
 - Platelet count $>$ 100,000/mm³
 - Absolute neutrophil count (ANC) \geq 1,000/mm³
 - Hemoglobin $>$ 11 g/dL
 - Serum transaminase [ALT or AST] \leq 1.2 x upper limit of normal (ULN)
 - Alkaline phosphatase \leq 1.2 x ULN
 - Serum creatinine \leq 1.2 x ULN

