4.0 Test Schedule

4.1 Test schedule for Chemotherapy-Induced Peripheral Neuropathy

Study Visit	1	2	3	4	5	6	7
Study Time Point	Screening /Baseline (Day -30 to Day 1)	Day 1	End of Week 1	End of Week 2 ^c (+3 Days)	End of Week 3	End of Week 4	End of study
CLINICAL ASSESSMENTS							
Informed consent	X						
Inclusion/exclusion criteria	X ^g						
Demographics/ Medical history	X						
Pregnancy testing ^a	X						
Randomization	X						
Dispense Study Product/Placebo		X		X			
Collect questionnaires							X
Adverse event assessment ^b			X	X	X	X	
STUDY TESTING							
EORTC QLQ-CIPN 20 instrument (Appendix I)	X		X	X	X	X	
Global impression of change (Appendix II)			X	X	X	X	
Chemotherapy Induced Peripheral Neuropathy Assessment Tool (Appendix III)	X		X	X	X	X	
Symptom experience diary (Appendix Va & Vb)	X ^d		X ^e	X ^e	X ^e	X ^e	
NCI-CTCAE neuropathy scale ^f (Appendix VI)	X		X	X	X	X	
Cycle = 14 days							
^a For individuals of childbearing potential. Must be done \leq 7 days prior to registration.							
^b Research nurse or clinician to call patient. Including inquiry about skin toxicity and to assess for suicidal thoughts (Appendix IX). Ask the patient if they have missed any doses of the study							

medication and provide education if necessary. Note any other pertinent information that the patient provides.

^c After subject completes week 2 they will turn in completed questionnaire diary and start the next supply of cream within 1-3 days after completing the first 2 weeks, ideally.

^d Appendix Va: System Experience Diary used for baseline assessment. Must be completed prior to application of study medication.

^e Appendix Vb: System Experience Diary used for weekly assessments. Must be completed at the end of each week.

^f To be completed during research nurse or clinician call to patient per Appendix VI.

^g Required Initial Laboratory Values per inclusion criteria 3.19c can be done any time after the patient has completed their chemotherapy and prior to study registration.

5.0 Stratification Factors:

- Gender (Male, Female, or Other)

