16.0 Statistical Considerations and Methodology

16.1 Primary

This is a randomized, two arm, placebo-controlled, double-blind, pilot study of whether CBD can improve CIPN more than a placebo. The purpose of this pilot study is to estimate the treatment effects of CBD compared to the placebo arm. These preliminary efficacy estimates will aid in the design of a large-scale randomized phase III clinical trial.

The primary endpoint is the change in CIPN from baseline to week 2. CIPN will be measured by the sensory subscale of the EORTC QLQ-CIPN20 which is composed of 9 individual items. Secondary endpoints include other measures of neuropathy as measured by the EORTC QLQ CIPN20 motor subscale, the EORTC QLQ CIPN20 autonomic scale, and the CTCAE neuropathy scale. Adverse event profiles will also be assessed using symptom questionnaires and the CTCAE 5.0.

As this is a pilot study, descriptive statistics and statistical plots will be utilized to summarize and estimate the primary and secondary endpoints. Statistical hypothesis testing will be used in an exploratory manner and will be interpreted accordingly.

For the primary analysis, changes in sensory neuropathy from baseline to week 2 will be compared between arms using two-sample, two-sided t-tests. The CBD arm will be compared to the placebo arm. We will construct 95% confidence intervals for the mean difference in sensory neuropathy score between arms. Repeated measures mixed models will be applied to the sensory scores over all time points to determine longitudinal effects and to adjust for confounding factors. Graphical results will include profile plots over time, stream plots of individual changes over time, and forest plots of the 95% confidence intervals by arm.

For logistical and financial reasons, the sample size for this pilot study is set at 40 patients (20 per treatment group). While this is only a descriptive study and is not powered to detect significant differences between arms, the following table provides power analyses for various effect sizes based on a two-sided, two-sample t test at $\alpha = 0.05$ for a fixed sample size of 20 patients per arm.

Effect size, $\Delta = \mu_1 - \mu_2 / \sigma$	0.5	0.6	0.7	0.8	0.9	1.0
Power	0.34	0.46	0.58	0.69	0.79	0.87

For example, we will have 79% power to detect an effect size of 0.9 in EORTC QLQ-CIPN20 with a sample size of 40 patients (20 per arm). This effect size is the mean difference divided by the common standard deviation within each arm.

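### Section 16.2 compares CTCAE neuropathy grades only by incidence and worst value, over an unstated window and without the baseline grade, which costs sensitivity to improvement

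*Combined protocol and SAP*

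**What the plan says.** Section 16.1 states: "Secondary endpoints include other measures of neuropathy as measured by the EORTC QLQ CIPN20 motor subscale", and continues with the autonomic scale and the CTCAE neuropathy scale. Section 2.2 gives the same list, ending with "the EORTC QLQ CIPN20 autonomic scale, and the total CTCAE neuropathy scale". In 16.1 a separate sentence deals with safety: "Adverse event profiles will also be assessed using symptom questionnaires and the CTCAE 5.0". CTCAE neuropathy is therefore listed as an efficacy measure.

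Section 16.2 then treats the listed scales differently. For two of them, "Analyses of the motor and autonomic subscales will be identical to the analyses of the primary endpoint", meaning change from baseline to week 2 with a 95% confidence interval, plus mixed models. For the third, the only applicable sentence is that analyses of "CTCAE grades and the symptom questionnaire individual items will compare the incidence and maximum (worst) values between arms", using Fisher's exact test for incidence and the Wilcoxon rank-sum test for the maximum. No window, baseline term or shift table is given, and the neuropathy scale has no rule separate from other CTCAE grades.

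The data for a baseline-referenced analysis are already planned. The section 4.1 schedule marks the "NCI-CTCAE neuropathy scale" at screening/baseline and at the end of weeks 1, 2, 3 and 4, and section 10.6 requires it at baseline and at each evaluation.

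**The concern.** Incidence and worst grade suit events that are absent at the start and may emerge. This endpoint is the reverse: patients enter with "At least 4 out of 10 severity of neuropathy pain and/or tingling per appendix IV", and the question is whether they get better.

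- **Incidence.** Appendix VI has no grade below I, and an answer of no problems scores Grade I. Any-grade incidence on that form would be at or near 100% in both arms. Incidence at a higher grade could be informative, but 16.2 does not specify one.
- **Maximum.** A patient no better at week 1 but better at week 2 keeps the week-1 grade as the worst value.
- **Window.** A maximum that includes baseline cannot fall below baseline. One over weeks 1-4 covers both treatments in every patient, because of the cross-over.
- **Baseline.** Without it, differences in severity between patients stay in the comparison as noise.

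The pilot's purpose makes this relevant: "These preliminary efficacy estimates will aid in the design of a large-scale randomized phase III clinical trial". An estimate that understates improvement is a weaker input to that design.

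**Working it through.** **1. The plan's own figure.** The plan gives no power for the CTCAE endpoint. Its table for the two-sample t-test (20 per arm, two-sided 5%) reproduces with the noncentral t distribution: 0.338, 0.456, 0.578, 0.693, 0.792, 0.869, against the stated 0.34, 0.46, 0.58, 0.69, 0.79, 0.87. Sample size and alpha below are taken from there.

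**2. Incidence.** Exact power of Fisher's test at 20 v 20 is 0 for 100% v 100%, 4% for 100% v 90% and 37% for 100% v 80%.

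**3. Worst grade against week-2 grade.** These inputs are assumptions, because the documents give no grade mix, response rate, onset or grade variability:

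- Baseline Grade I/II/III in 35/50/15%.
- Of patients able to improve (Grade II or III, 65%), 70% v 15% improve by one grade at week 2. Over all patients this is 0.65 × 0.70 = 45.5% v 0.65 × 0.15 = 9.75%, about 45% v 10%.
- Week-1 response among those able to improve: 30% v 10% (late), 50% v 12% (intermediate) or 70% v 15% (complete by week 1).
- Each recorded grade shifts by one with probability s.

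Rejection rates (6,000 simulated trials per scenario):

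| s | Worst grade wk 1-2: late / intermediate / complete by wk 1 | Change to wk 2, rank-sum | Wk-2 grade, ANCOVA on baseline |
|---|---|---|---|
| 0 | 10 / 23 / 44% | 74-75% | 82% |
| 0.1 | 10 / 20 / 37% | 50% | 59% |
| 0.2 | 10 / 20 / 32% | 33-34% | 43-45% |
| 0.3 | 10 / 17 / 28% | 24-25% | 33-34% |

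Repeat runs differ by about a point. With no true difference (15% v 15%), ANCOVA rejected in 3.7-5.1%.

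**4. Which feature costs what.** Late onset, s = 0 / 0.1 / 0.2 / 0.3 (3,000 trials each):

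| Analysis | Rejection rate |
|---|---|
| Worst grade | 9 / 10 / 10 / 10% |
| Worst grade, adjusted for baseline | 22 / 16 / 13 / 13% |
| Week-2 grade, no baseline | 41 / 38 / 33 / 25% |
| Week-2 grade, adjusted for baseline | 82 / 58 / 45 / 32% |

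With late onset, dropping the maximum recovers more than adding baseline. With response complete by week 1 and s = 0, worst grade and week-2 grade coincide, so the rise from 44% to 82% is due to baseline alone. At s = 0.2 or 0.3, adding baseline to worst grade gains about 9-11 points.

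**5. The estimate.** With s = 0, and patients who improve at week 1 staying improved, the week-2 mean difference is 0.65 × (0.70 − 0.15) = 0.358 grade. The worst-grade difference is 0.65 × (0.30 − 0.10) = 0.130 (late, ratio 0.36), 0.65 × (0.50 − 0.12) = 0.247 (intermediate, ratio 0.69) or 0.358 (complete by week 1, ratio 1.00). Over 72 scenarios (three grade mixes, two response levels, three onsets, four values of s) the ratio was 0.28-0.58, 0.66-0.85 and 1.00-1.12 respectively.

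**6. A different model.** Grades were cut from a correlated normal variable with an assumed effect of 0.9 SD and between-visit correlation ρ = 0.3 / 0.5 / 0.7 / 0.85.

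| Power | Full effect in both weeks | Effect only by week 2 |
|---|---|---|
| Worst grade wk 1-2 | 80 / 77 / 75 / 71% | 17 / 14 / 12 / 9% |
| Same, adjusted for baseline | 82 / 86 / 91 / 96% | 19 / 18 / 16 / 13% |
| Week-2 grade, adjusted | 69 / 75 / 85 / 93% | 70 / 74 / 85 / 93% |

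A maximum that includes baseline had 14-32% power (effect in both weeks) or 6-10% (week 2 only). A maximum over weeks 1-4 had about 5%.

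**7. Why adjust rather than subtract.** Relative to the post-treatment value alone, the variance of simple change is 2(1 − ρ) and of the adjusted analysis 1 − ρ². At ρ = 0.3 these are 1.40 and 0.91; at ρ = 0.7, 0.60 and 0.51. Change helps only above ρ = 0.5.

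**The case against.** The case on the other side has substance.

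- **A reader might infer that the planned comparison is invalid or cannot show benefit.** It is neither. Arms are randomised, so worst grade within the first period is a fair comparison. With a full effect in both weeks, the second model gives it 71-80% power.
- **A reader might infer that omitting baseline is the main fault.** Step 4 shows otherwise for late onset, where the maximum does more of the damage.
- **The size rests on assumptions.** When response is complete by week 1 and s = 0.3, the gap is 28% against 33-34%, and the worst-grade estimate is not understated. In the second model, with a full effect in both weeks and ρ of 0.3 or 0.5, worst grade beats the adjusted week-2 grade (80 v 69%, 77 v 75%), because it draws on two readings. The first model, where adjustment won in all 72 scenarios, does not establish a universal advantage.
- **Secondary analyses are descriptive.** Section 16.1 promises summaries and plots, and three CIPN20 scales get baseline-to-week-2 analyses. This limits the consequence, but no baseline-referenced CTCAE summary is promised.
- **The 16.2 sentence may be meant for adverse events only.** Then the listed endpoint has no stated comparison, and the same edit is needed.
- **Section 10.61 need not contradict 6.4 and 10.6.** It says pretreatment symptoms need no grading, but it can be read as the general rule, with neurotoxicity as the specific exception. It needs clarifying and is not proof that baseline grades will be missing.

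**Conclusion.** The point holds as a loss of sensitivity in one exploratory secondary endpoint. The stated comparison takes a maximum over an undefined window and ignores a baseline grade that is already scheduled. The maximum costs more when benefit builds after week 1; the missing baseline costs more when response is early and grades are stable.

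Under the assumptions in step 3, rejection rates are about 9-11% (late onset) to 28-44% (complete by week 1) for worst grade, against about 33-83% for the adjusted week-2 grade. The loss is large with late onset, small with early onset and noisy grades, and can reverse under the second model. The choice of week 2 therefore rests also on consistency: it is the plan's primary time point and the one used for the other neuropathy scales.

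The documents do not support a claim that the trial's conclusions are biased. CIPN20 results are unaffected. Confidence in the size is moderate at best, because no grade distribution, onset or variability is documented.

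**What to change.** In section 16.2:

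1. Separate CTCAE neuropathy from other adverse events.
2. Compare the week-2 grade between arms adjusted for baseline grade (ANCOVA or an ordinal model), with a 95% confidence interval.
3. Add, as description, a baseline-to-week-2 shift table and the number of patients entering at Grade I, who cannot register improvement on this form under any analysis.
4. Keep incidence and worst grade for other adverse events, and state that the window lies within one treatment period.

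As minor wording points, state that 10.61 does not override the baseline neurotoxicity grading in 6.4 and 10.6, and reconcile the Appendix VI Grade I label (asymptomatic) with its sample answers, which allow some tingling.

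The analysis change costs SAP wording only, because baseline and weekly grades are already scheduled. The other points need one clarifying sentence and a check of the form. No patients, visits or measurements are added.

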Appendix Vb: Symptom Experience Diary —During Treatment

Please circle **ONE** number for each item that best describes you over the past 7 days.

1. Over the past week, please rate your quality of life:

2. Do you have any skin rash on your hands or feet:

3. How many doses of the study medication do you think that you missed over the past week?
(Circle one answer)

0 times 1-2 times 3-4 times More than 5 times

4. Did you have any skin side effects from the study product?

No

Yes, if so, please describe the symptom(s) and severity:

5. Did you have any other side effects from the study product?

No

Yes, if so, please describe the symptom(s) and severity:

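### Section 16.2 puts the diary's quality-of-life rating through an incidence comparison that has no meaning without a cut-off, and leaves its baseline rating unused (minor)

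*Combined protocol and SAP*

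**What the plan says.** Section 16.2 sets one rule. For CTCAE grades and for each item of the symptom questionnaire, the analysis will "compare the incidence and maximum (worst) values between arms". The tests follow: "Fisher's exact tests will be used to compare incidence rates and Wilcoxon rank-sum tests will be used to compare maximum values between arms".

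The Symptom Experience Diary is the only symptom questionnaire in the Section 4.1 schedule. Section 16.2 does not name it, so the link is an inference. Item 1 reads "Over the past week, please rate your quality of life", with the same wording at baseline (Appendix Va) and weekly on treatment (Appendix Vb). The respondent circles one "number for each item that best describes you over the past 7 days". The response scale for item 1 does not appear in the text available here. The baseline diary is mandatory: "System Experience Diary used for baseline assessment. Must be completed prior to application of study medication".

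Two other statements give context. Section 16.1 ties these questionnaires to safety: "Adverse event profiles will also be assessed using symptom questionnaires and the CTCAE 5.0". Section 16.2 treats the other patient-reported scores differently: "Analyses of the motor and autonomic subscales will be identical to the analyses of the primary endpoint". That means change from baseline, a 95% confidence interval and a mixed model. Section 16 gives no other analysis of diary item 1.

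**The concern.** Incidence and worst grade are natural summaries for rash, side effects and CTCAE grades, where zero means absent and a higher number is worse. A quality-of-life rating has neither property by default: every patient who completes the diary has a value every week, and which end is bad depends on the anchors. The rule also gives no role to a baseline rating that all patients must supply.

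Section 16.1 says the pilot is meant to supply estimates for a phase III design. For this item the plan yields one comparison with no defined event and one that is less precise than the collected data allow. The event definition, scale direction and analysis window would then have to be settled later, possibly after the data have been seen.

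**Working it through.** **The plan's own figure.** Section 16.1 gives power for a two-sided two-sample t test, alpha 0.05, 20 per arm. The noncentral t gives 0.338, 0.456, 0.578, 0.693, 0.792 and 0.869 at effect sizes 0.5 to 1.0, which matches all six entries (0.34, 0.46, 0.58, 0.69, 0.79, 0.87). The table concerns the primary endpoint and is not in question. The documents state no power, SD or correlation for the quality-of-life item, so the rest is illustrative.

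**Incidence.** Assume a 0–10 scale, mean 6, SD 2, rounded to whole numbers. The chance of a zero in one week is P(Z < (0.5 − 6)/2) = P(Z < −2.75), about 0.003. Taking incidence as any score above zero, simulation put about 100% of both arms in the event group, and Fisher's test had power of about 0. Any other cut-off would have to be invented, because Section 16.2 states none.

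**Validity of the rank-sum test.** With no treatment effect, the rank-sum test on the worst of weeks 1–2 rejected in 0.036 to 0.056 of simulated trials (2,000 per setting). The type I error is sound.

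**Precision.** Assume unit SD, an equal correlation ρ between baseline, week 1 and week 2, a 0.7 SD shift in both weeks, and 20 per arm.

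- Residual variance of week 2 given baseline: 1 − ρ².
- Residual variance of the weeks 1–2 mean given baseline: (1 + ρ)/2 − ρ².
- Standardised effect for the adjusted mean: 0.7 divided by the square root of that variance.

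| ρ | Rank-sum on maximum (simulated) | Week 2, baseline-adjusted (simulated) | Residual variance of adjusted mean | Standardised effect | Power of adjusted mean (noncentral t) |
|---|---|---|---|---|---|
| 0.2 | 0.70 | 0.59 | 0.60 − 0.04 = 0.56 | 0.935 | 0.82 |
| 0.3 | 0.68 | 0.60 | 0.65 − 0.09 = 0.56 | 0.935 | 0.82 |
| 0.5 | 0.62 | 0.69 | 0.75 − 0.25 = 0.50 | 0.990 | 0.86 |
| 0.6 | 0.60 | 0.75 | 0.80 − 0.36 = 0.44 | 1.055 | 0.90 |
| 0.7 | 0.60 | 0.85 | 0.85 − 0.49 = 0.36 | 1.167 | 0.95 |
| 0.8 | 0.59 | 0.95 | 0.90 − 0.64 = 0.26 | 1.373 | 0.99 |

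The closed form is slightly optimistic because it ignores estimation of the baseline slope. Simulated power for the adjusted mean runs from about 0.81 to 0.98 (0.89 at ρ = 0.6). Week 2 alone, adjusted, ties with the maximum near ρ = 0.4 and is better only from about 0.5.

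**Source of the gain.** In one set of simulated trials at ρ = 0.5/0.6/0.7, rank-sum on the maximum had power 0.63/0.62/0.60. Without baseline, rank-sum on week 2 had 0.56/0.57/0.55 and a t test on week 2 had 0.58/0.59/0.58. Using the maximum therefore loses nothing against an unadjusted week 2 score. At ρ = 0.6, adjusting the worst value itself for baseline raises power from 0.60 to 0.85. The gain comes from using the baseline together with both weeks.

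**Window.** Section 16.2 names no weeks for the maximum. Section 2.0 crosses every patient over after 14 days, so a maximum over weeks 1–4 would mix both treatments.

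**The case against.** Three points on the other side have force.

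- **Purpose.** The questionnaires serve the adverse-event profile, where a worst value is defensible. A week 2 analysis alone could miss harm: at ρ = 0.6, a 1 SD drop in week 1 that has gone by week 2 is detected by adjusted week 2 at about chance level (0.05), against about 0.6 for the true worst value. This stands, and it is why the fix uses both weeks. The adjusted mean shifts by 0.5 SD, a standardised effect of 0.5/√0.44 = 0.754, with power of about 0.63.
- **Direction.** A reader might infer that the plan compares each patient's best week and so hides harm. The documents do not support that. The scale cannot be seen here, and the word in parentheses in Section 16.2 suggests that the worst end is intended whatever the coding. The most that can be said is that the direction should be written down.
- **Validity and power.** A reader might also infer that the tests are wrong for a rating, or that taking a maximum always loses power. Neither holds. Rank-sum suits an ordinal rating, randomisation protects the comparison when baseline is left out, and at low correlation the maximum beats adjusted week 2.

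The item is also not a named endpoint, and Section 16.2 calls these analyses descriptive. That limits the importance but does not make incidence meaningful or give the baseline rating a use.

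**Conclusion.** The point holds in a limited form and is minor. Two things follow from the text, given the inference that the diary is the symptom questionnaire meant: incidence is undefined for the quality-of-life rating, and the baseline rating that patients must provide is not used. The second costs precision and introduces no bias.

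The size depends on assumptions that the documents do not supply: equal correlation between assessments, roughly normal scores and a 0.7 SD shift in both weeks. Under them, the baseline-adjusted weeks 1–2 mean beats the planned rank-sum test at every correlation from 0.2 to 0.8. The margin is about 0.1 in power at the low end and about 0.4 at the high end. No stated objective, the primary analysis or the sample size changes.

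**What to change.** In Section 16.2:

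1. Remove diary item 1 from the incidence comparison.
2. Compare quality of life between arms over weeks 1–2, before the cross-over, using both weeks and adjusting for the baseline rating, and report the difference with a 95% CI. Adjustment is preferable to a change score, whose variance relative to a single post-treatment score is 2(1 − ρ) and exceeds 1 when ρ is below 0.5.
3. Where a worst value is also reported, take it within weeks 1–2 and at the worst end of each item's scale, with that end stated.
4. Keep incidence and worst value for the rash and side-effect items.

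The cost is a sentence or two in the plan and one small model for an exploratory item. No new data are needed.
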